Our principal aim is to determine whether a novel biopsychosocial intervention following opioid overdose (OD) affects 1) the frequency of secondary opioid OD events and 2) the proportion of individuals who remain engaged in treatment for opioid use disorder (OUD) or are in remission at 30 days and at 180 days post consent. We define remission as engagement in daily medication-assisted therapy (MAT)—typically buprenorphine/naloxone (BUP) or methadone—and/or a recovery capital score of ≥ 27.5 .¹ Our intervention will connect individuals with important community resources that hopefully will facilitate progress toward long-term recovery. Specifically, we will link individuals with moderate-severe OUD, who have experienced at least 1 opioid OD requiring naloxone resuscitation but refused BUP treatment, if offered, with 1) treatment with BUP, 2) methadone maintenance, intensive outpatient, or residential treatments, or 3) education materials from the Connecticut Community for Addiction Recovery (CCAR). Enrolled participants may switch from 1)-3) throughout. To carry out the intervention, an addiction recovery coach from CCAR and a health educator (research) paramedic will form a team (RCP team) and perform remote (including over-the-phone) and/or electronic follow-up visits after a participant has experienced at least 1 opioid OD requiring naloxone resuscitation. Our hypothesis is that the intervention, by the RCP team, connecting participants to community resources will decrease subsequent OD events and increase the likelihood of remission. To evaluate this hypothesis, data will be collected from self-report and from EPIC, Yale New Haven Hospital's (YNHH) medical record system. If the sources of information appear to conflict, then what is entered in EPIC will take precedence.

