Our secondary aim is to determine whether the intervention affects 1) the frequency of positive-urine tests for opioids and 2) the frequency and proportion of subjects self-reporting opioid use. (We recognize that, due to constraints on in-person follow-up imposed by the COVID-19 pandemic, individuals who are most likely to get urine tests are those who are in treatment and those who might subsequently present to the emergency department (ED) for opioid-related complaints.) Our hypothesis is that our intervention will decrease both. As in the previous aim, data will be collected remotely/electronically from self-report and EPIC. If the sources of information were to conflict, then what is entered in EPIC will take precedence.

Data from our entire cohort will be compared in aggregate with patients who were started on BUP in the ED over the same time period and with historic controls who received only printed resources addressing OUD as reported in [name] et al.¹¹

2. Probable Duration of Project: State the expected duration of the project, including all follow-up and data analysis activities.

The probable duration of the project is 2 years (from 09/2019-09/2021). There is potential for extension after this time, depending on availability of funding.

3. Background: Describe the background information that led to the plan for this project. Provide references to support the expectation of obtaining useful scientific data.

Importance of problem.

The epidemic of opioid use disorder (OUD) prompted a presidential declaration of a public health emergency in October, 2017, and it was extended in January, 2018.² In 2016, an unprecedented 63,632 deaths in the United States (US) were attributed to drug overdose; 2/3 of these involved opioids.³ The deaths due to drug overdose in 2016⁴ exceeded the number of traffic fatalities during the peak year of 1972,⁵ the number of HIV deaths at their peak in 1995, the final year before the introduction of triple antiviral therapy,⁶ and the peak year for gun violence in the US, which was 1993.^{7,8} Nonfatal opioid overdoses are highly associated with ongoing OUD and recurrent overdoses. One study reviewing emergency medical service (EMS) records of

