To date, there is no standard of care for individuals with OUD who have overdosed on opioids, have been resuscitated by naloxone, and have refused BUP treatment. As noted in the previous section, YNHH typically will send home these individuals with OEN kits. However, follow-up care remains variable. Hence, we seek to determine whether individuals with OUD might benefit significantly from a novel, team-based intervention encouraging biopsychosocial and medical interventions. Our intervention will connect participants with important community resources that we expect will facilitate progress toward long-term recovery. Specifically, we will link individuals with moderate-severe OUD, who have experienced at least 1 opioid OD requiring naloxone resuscitation but who refused BUP treatment in the ED, if offered, with 1) treatment with BUP, 2) methadone maintenance, intensive outpatient, and/or residential treatment, or 3) education materials from CCAR. Enrolled participants may switch from 1)-3) throughout.

We wish to assess whether our intervention connecting participants to community resources affects 1) the frequency of secondary opioid OD events and 2) the proportion of individuals who remain engaged in treatment for OUD or are in remission at 30 days and at 180 days post consent. We define remission as engagement in daily medication-assisted MAT—typically BUP or methadone—and/or a recovery capital score of ≥ 27.5 . Our hypothesis is that the intervention by the RCP team will decrease subsequent OD events and increase the likelihood of remission. We also seek to determine whether the intervention affects 1) the frequency of positive-urine tests for opioids and 2) the frequency and proportion of subjects self-reporting opioid use. Our hypothesis is that our intervention will decrease both.

We will conduct our study as follows (Figures 1 & 2 below):

To prepare for the intervention, health educator paramedics and key study staff are required to attend 12 hours of in-person training, which is to take place over at least 2 days, to learn about best practices assessing those with OUD. [name], co-PI of this study, along with CCAR staff, will teach. Sessions will include training to conduct a brief negotiation interview (BNI) and a brief assessment of recovery capital (BARC-10) interview. Training also will prepare all staff to respectfully ask questions about potential overdose events and the possibility of creating and/or implementing a wellness plan.

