Consent may be obtained at the ED, during community outreach events, electronically in a Yale School of Medicine version of REDCap®, or remotely (e.g., via email or picture), in accordance with University guidelines issued on 05/21/2020 from the Yale Center for Clinical Investigation. After consent and study initiation, either at the hospital or at some other time, the RCP team will perform a BNI—whose goal is to employ motivational techniques to help those with substance abuse consider their reasons for wanting to address dependency. Electronically, the RCP team will perform psychosocial and medical evaluations. (Please see the document, *Survey Tool and Handbook*, for details. It is included in our submission materials.) The RCP team will enter all data into a secured, encrypted database, REDCap®. To obtain consent or approximately 30 days after consent, the RCP team will schedule an electronic/remote (including by phone) Meeting 1 with participants. During this time, by remote interventions, the RCP team will collect and enter data into REDCap® based on discussions with and evaluations of participants. During an electronic/remote (including by phone) Meeting 2, which should occur no more than 180 days after consent, the RCP team will also collect and enter data into REDCap® based on discussions with and evaluations of participants. The study team will also enter data from participants' medical records at all time intervals. It is important to underscore that, due to the coronavirus pandemic, electronic and remote (including by phone) modalities will be utilized to the greatest extent possible.

Data from the entire cohort will be compared in aggregate with patients who were started on BUP in the ED over the same time period and with historic controls.¹¹

Figure 1. Screening + Enrollment

Genetic Testing N/A

A. Describe

- i. the types of future research to be conducted using the materials, specifying if immortalization of cell lines, whole exome or genome sequencing, genome wide association studies, or animal studies are planned *Write here*
 - ii. the plan for the collection of material or the conditions under which material will be received *Write here*
 - iii. the types of information about the donor/individual contributors that will be entered into a database *Write here*
 - iv. the methods to uphold confidentiality *Write here*

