
- d. For multi-site studies for which the Yale PI serves as the lead investigator: N/A
 - i. How will adverse events and unanticipated problems involving risks to subjects or others be reported, reviewed and managed? N/A
 - ii. What provisions are in place for management of interim results? N/A
 - iii. What will the multi-site process be for protocol modifications? N/A

12. **Statistical Considerations:** Describe the statistical analyses that support the study design.

Study design

Primary outcomes

The primary outcomes will be 1) percentage of individuals with repeat opioid overdose events requiring naloxone resuscitation, identified using YNHH's electronic medical record system (EPIC), and 2) percentage of individuals engaged in any treatment for OUD or who are in remission. Data will be recorded at baseline and at 30 and 180 days after consent to participate in the research.

Secondary outcomes

The secondary outcomes will be 1) frequency and percentage of individuals with positive opioid tests (urine) recorded in their hospital charts or during medication program monitoring, and 2) frequency and percentage of subjects with self-reported opioid use. Data will be recorded at baseline and at 30 and 180 days after consent to participate in the research.

Statistical analyses

We will document demographics (sex, race/ethnicity, age, education, employment status, etc.) and clinical characteristics (e.g., heroin use, non-opioid use in the past 6 months, lifetime treatment for addiction etc.) among all cohorts. χ^2 tests (2 df) will be employed to detect statistically significant differences.

Group	X	No X	Total
PRIDE + CCAR intervention			
BUP-initiated in ED after OD			
Historical control(s)			
Total			

For primary outcomes, "X" is % of repeated overdose events or % of treatment engagement. For secondary outcomes, "X" is frequency or % positive testing for opioid tests or % (self-reported) opioid abuse.

Sample size determination

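### Primary outcome 2 is declared as engagement or remission but tabulated as engagement alone, and no recovery capital score is planned for either comparator cohort

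*Combined protocol and SAP*

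**What the plan says.** The combined protocol and SAP describes the second primary outcome in three places.

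- **Statement of aims**, repeated in substance in item 4 (Research Plan): the proportion of people "who remain engaged in treatment for opioid use disorder (OUD) or are in remission at 30 days" and at 180 days.
- **Item 12, Primary outcomes:** the "percentage of individuals engaged in any treatment for OUD or who are in remission".
- **Item 12, Statistical analyses, note to the three-group table:** for primary outcomes, X "is % of repeated overdose events or % of treatment engagement". Remission is not mentioned.

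The aims and item 4 define remission as engagement in daily MAT "and/or a recovery capital score of" at least 27.5.

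On measuring recovery capital, the only instrument named is in the staff-training paragraph of item 4: "Sessions will include training to conduct a brief negotiation interview (BNI) and a brief assessment of recovery capital (BARC-10) interview". For enrolled participants, item 4 adds: "Electronically, the RCP team will perform psychosocial and medical evaluations". Details are left to a survey handbook that is not among the documents.

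On comparators, item 4 states: "Data from the entire cohort will be compared in aggregate with patients who were started on BUP in the ED" over the same period, and with historical controls. The aims describe the latter as "historic controls who received only printed resources addressing OUD as reported in" a published randomised trial.

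**The concern.** The declared outcome and the tabulated outcome differ by one component, and that component is the one with no planned source in either comparator. The cohorts are not randomised, so a between-cohort comparison needs at least an outcome that is ascertained in the same way in each cohort.

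If the outcome text governs and the score exists only in the RCP cohort, people outside treatment can count as successes there and nowhere else. The comparison then moves in favour of RCP for a reason unrelated to treatment engagement. If the table note governs, this asymmetry does not arise, but the analysis is not of the outcome set out in the aims. Either way, item 12 needs a correction.

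**Working it through.** The plan states no rate for this outcome, and its sample size of about 100 is not tied to either wording. There is therefore no plan figure to reproduce. The check is one of definitions, followed by a simple sizing.

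**Step 1. What remission adds.** Let E be engaged in any treatment, M be on daily MAT, and S be a score of at least 27.5. Remission is M or S, so the declared outcome is E or M or S. Anyone in M is already in E. The outcome therefore reduces to E or S, which is E plus those who are not in E but are in S. The recovery capital score is the whole of what remission contributes.

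**Step 2. Where S is planned.**

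| Cohort | Source of S in the document |
|---|---|
| RCP participants | Inferred: staff are trained in BARC-10, and participants are evaluated by the RCP team |
| Concurrent ED-buprenorphine patients | None stated |
| Historical controls | None stated; taken from a published trial |

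For all cohorts together, item 12 mentions only demographics and clinical characteristics, and recovery capital is not among its examples. A second inference is also involved. The 27.5 threshold is referenced to a paper on the assessment of recovery capital, and nothing states that BARC-10 is the instrument to which it applies.

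**Step 3. Size if S is counted in RCP only.** With engagement p, and a share r of the non-engaged reaching the score:

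RCP rate = p + (1 − p)r, so the addition is (1 − p)r.

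The value of r is purely assumed. For p, the Background says that less than half of patients starting buprenorphine remain engaged, and that this is roughly double the proportion after a brief interview or community referral. Taking 45% for buprenorphine gives 45/2 = 22.5% for the others. This too is an assumption, because the historical controls are described as receiving printed resources. At p = 22.5%, for example, (1 − 0.225) × 0.05 = 0.039 and (1 − 0.225) × 0.20 = 0.155. Percentage points added:

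| p | r = 5% | r = 10% | r = 20% |
|---|---|---|---|
| 15% | 4.3 | 8.5 | 17.0 |
| 22.5% | 3.9 | 7.8 | 15.5 |
| 30% | 3.5 | 7.0 | 14.0 |
| 45% | 2.8 | 5.5 | 11.0 |

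**Step 4. How much of that is artefact.** If the target is the composite, the error in RCP minus comparator is the part omitted from the comparator, (1 − p_c)r_c, where the subscript c marks the comparator's values. It equals (1 − p)r only when engagement and recovery capital are the same in both cohorts. Building recovery capital is a stated goal of the coaches (Background, Innovation), so some of the RCP addition could be a real effect. Without the score in a comparator, the two cannot be separated.

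**The case against.** **The tested variable is named.** A reader might infer that the plan never says what is tested. That goes too far: the table note does name treatment engagement, and under that reading the asymmetry disappears. What stands is the mismatch with the declared outcome. The note may be shorthand, because it also loosens the first primary outcome from individuals with a repeat overdose to repeated overdose events. It therefore cannot be relied on to settle the matter.

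**The bias is conditional.** A reader might infer that the planned analysis will favour RCP. The document does not support that as a certainty. The outcome text would have to govern, the score would have to be collected in RCP, and the comparators would have to be scored on engagement alone. A composite that cannot be computed in a cohort might instead be left uncompared. This objection stands, and the conclusion is worded accordingly.

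**False-positive rates.** A reader might infer a badly inflated error rate. With all three cohorts at 22.5% engagement, 100 per cohort and r = 20%, the 2-df test would reject 71% of the time instead of 5%. That null conflicts with the Background, which puts buprenorphine engagement at roughly double. With ED-buprenorphine at 45% and the others at 22.5%, the test already rejects 95% of the time with no score counted. It then rejects 91%, 88%, 89% and 96% of the time at r = 5%, 10%, 20% and 30%. A non-directional test does not measure bias towards RCP, the comparator sizes are not stated, and r has no source. These rates should carry no weight in judging severity.

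**Another repair exists.** Collecting the score prospectively in the concurrent ED-buprenorphine patients would also restore comparability for that pair. This is fair, and the fix below allows it.

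**Conclusion.** The point holds as a mismatch in the definition of a primary outcome, together with a component that has no planned source in either comparator. Both follow directly from the text and depend on no assumed number. The possible distortion is conditional: if the declared composite is tested with the score available only in RCP, the RCP rate gains (1 − p)r with no counterpart. At an assumed p of 22.5%, that is 3.9 points at r = 5% and 15.5 points at r = 20%. The direction is clear under that condition, but the size is unknown because nothing in the document informs r. That RCP participants are scored at all, and that BARC-10 supplies the 27.5 threshold, are inferences. The survey handbook could confirm either, although item 4 cites it only for evaluations by the RCP team. This should be corrected before any between-cohort analysis.

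**What to change.** Reconcile item 12 so that the outcome text and the table note agree, and the between-cohort test of primary outcome 2 is of treatment engagement. Give one written definition of engagement and a stated data source, applied identically to every cohort compared at each time point. The Background mentions engagement only at 30 days when citing the trial that supplies the historical controls. The day-180 source should therefore be stated for each cohort, or that comparison limited to cohorts that have one. The definition should also say whether receiving education materials alone counts as treatment; that choice is the investigators'.

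Report the composite that includes the recovery capital score within the RCP cohort, naming the instrument to which the 27.5 threshold belongs. Compare it between cohorts only where the score is collected in the comparator as well.

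The cost is a few sentences of wording plus a stated source of ascertainment for each cohort. The downsides are a between-cohort outcome narrower than the aim and a lower headline rate in the RCP cohort.

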For this study, the following individuals, funding, and/or regulatory agencies will be notified: all co-Investigators listed on the protocol, the Data Safety and Monitoring Board, the Yale HIC, and the Centers for Disease Control. The principal investigators ([name], and [name]) will conduct a review of all adverse events upon completion of every study subject. They will evaluate the frequency and severity of the adverse events and determine if modifications to the protocol or consent form are required. The risks associated with participating in this study can be categorized as minimal. The Data and Safety Monitoring Plan (DSMP) template of the Yale University School of Medicine includes provisions for data review and performance of safety reviews, as described below. Data and safety monitoring procedures in this study include secure computerized data collection and monitoring systems and an organizational structure of clearly defined tasks assigned to all research and clinical personnel involved in the conduct of this study. The computerized study tracking system consists of a data base system that records research activities including enrollment and follow-up activities (assessments, urine collection, and treatment clinic attendance) and allows monitoring of drug use through inclusion of the results of urine toxicology testing. The PIs will use this database to monitor ongoing subject participation. The organizational structure used to ensure quality of data in this project include extensive training and close supervision of clinical staff and research paramedics in data collection, and preliminary review of collected data by study personnel for completeness and accuracy. Research paramedics will computerize collected study data using encrypted tablets with specialized software (Zoom 5.0. REDCap®, EPIC telehealth, SPSS Data Entry, etc.) facilitating efficient data entry and allowing elimination of out-of-range values and double entry of data for detection of key punch errors. All error corrections will be fully documented in the research records of the study. All research personnel are required to successfully complete the Yale Human Investigation Committee initial and ongoing training in protection of human subjects and the responsible conduct of scientific research. All clinical aspects of the study that take place in a YNHH ED, such as treatment delivery and monitoring of subjects' progress, are also fully documented and supervised by the PIs. Drs. [name] and [name] will meet monthly to review the overall progress of the patients receiving BUP treatment. All members of the research team are familiar with procedures for identifying and reporting possible adverse events.

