Our research is funded by an R01 through the CDC, which no longer issues hardcopy Certificates of Confidentiality (CoCs). However, as noted above, per section 2012 of the 21st Century Cures Act, a CoC "automatically" has been issued by the agency.

<https://www.cdc.gov/od/science/integrity/confidentiality/applinst.htm>

SECTION V: POTENTIAL BENEFITS

Potential Benefits: Identify any benefits that may be reasonably expected to result from the research, either to the subject(s) or to society at large. (Payment of subjects is not considered a benefit in this context of the risk benefit assessment.)

Participants are expected to directly benefit from the educational, counseling, and medical resources and contacts. We expect that this will provide better outcomes in the short- and possibly long-terms.

SECTION VI: RESEARCH ALTERNATIVES AND ECONOMIC CONSIDERATIONS

1. **Alternatives:** What other alternatives are available to the study subjects outside of the research? Participants may decline study participation or participate in another study. BUP can be started in the ED for individuals willing to accept it at the time of an OD. Other resources for harm reduction and treatment are routinely provided at the time of an ED visit, but are seldom associated with positive short-term outcomes.

2. **Payments for Participation (Economic Considerations):** Describe any payments that will be made to subjects, the amount and schedule of payments, and the conditions for receiving this compensation.
Participants will receive 3 payments of \$25 (for a total of \$75) after consent and after the first and second meetings. Each payment is given as a \$25 gift card to Stop & Shop. Initial payments may be obtained upon consent in the ED; subsequent payments will be mailed or provided electronically, according to subjects' preferences.
3. **Costs for Participation (Economic Considerations):** Clearly describe the subject's costs associated with participation in the research, and the interventions or procedures of the study that will be provided at no cost to subjects.
The research will not generate any costs to participants, as we expect that study personnel will meet with them at settings and times of participants' choosing and convenience. All medical and laboratory testing is part of participants' routine care and is not directly a feature of the research itself. Additionally, for those electing to receive BUP, grant funding will cover its cost.

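### Urine positives come only from routine-care tests, so the planned group comparison mixes differences in testing with differences in use, with a bias of unknown direction

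*Combined protocol and SAP*

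**What the plan says.** Item 12 (Statistical Considerations, Secondary outcomes) names as its first secondary outcome the "frequency and percentage of individuals with positive opioid tests (urine) recorded in their hospital charts or during medication program monitoring", at baseline, 30 and 180 days. Under Statistical analyses, chi-square "tests (2 df) will be employed to detect statistically significant differences". The table there has three rows (intervention cohort, patients started on buprenorphine in the ED, historical controls) and the columns X, No X and Total. For this outcome X is a frequency or a percentage positive. No denominator is stated, and there is no column for people without a test.

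Item 1 gives the expected direction for the two secondary outcomes: "Our hypothesis is that our intervention will decrease both". In the same paragraph it concedes that "individuals who are most likely to get urine tests are those who are in treatment and those who might subsequently present to the emergency department" with opioid-related complaints. It also lets EPIC prevail when sources conflict.

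On whether urine is collected for the study, two places differ. Section VI (Costs for Participation) calls laboratory testing "routine care and is not directly a feature of the research itself". Item 11 (Data and Safety Monitoring Plan) describes a tracking system that covers "follow-up activities (assessments, urine collection, and treatment clinic attendance", but gives no schedule.

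The principal hypothesis in item 1 is that the intervention will "decrease subsequent OD events and increase the likelihood of remission". Remission there is defined partly as engagement in medication-assisted therapy.

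**The concern.** A recorded positive needs two things: opioid use and a test. The plan wants to learn about the first, but the second depends on being in treatment, which is a primary outcome and the thing the recovery teams work to change. If engagement differs between groups, testing differs too, and the X / No X comparison cannot separate the two. The caveat in item 1 describes this, but item 12 has no rule for untested people, no report of testing rates and no adjustment or sensitivity analysis.

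The definition of a positive is also open. Results may come from medication-program monitoring, and the plan does not say how a prescribed agonist is handled.

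At stake is whether the secondary hypothesis of fewer positive tests gets an interpretable answer. A real reduction in use could be hidden or appear as an increase, and against some comparators a worse result could look better.

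**Working it through.** The documents give no testing rate, positivity rate or expected difference for this outcome, so there is no plan figure to reproduce. **All rates below are assumptions.** The nearest anchor is in item 3: fewer than half of buprenorphine starters remain engaged, roughly double the proportion under brief interview or referral.

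**Model.** Let *e* be the share engaged, *te* and *tn* the probability of being tested if engaged or not, and *pe* and *pn* the probability of use (and so of a positive if tested).

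- True use = e·pe + (1−e)·pn
- Recorded positives, all persons as denominator = e·te·pe + (1−e)·tn·pn
- Positives among the tested = recorded ÷ [e·te + (1−e)·tn]

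**Assumed rates:** te = 1.0, tn = 0.2, pe = 0.3, pn = 0.7.

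| Engaged | True use | Recorded, all persons | Tested | Positive among tested |
|---|---|---|---|---|
| 30% | 0.09 + 0.49 = 58% | 0.09 + 0.098 = 18.8% | 44% | 18.8/44 = 42.7% |
| 45% | 0.135 + 0.385 = 52% | 0.135 + 0.077 = 21.2% | 56% | 21.2/56 = 37.9% |
| 60% | 0.18 + 0.28 = 46% | 0.18 + 0.056 = 23.6% | 68% | 23.6/68 = 34.7% |

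*Less engaged comparator (30%) v intervention (60%):* true use falls by 12 points, while recorded positives rise by 4.8.

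*Intervention (30%) v ED buprenorphine starters (45%):* the intervention has 6 points more true use but 2.4 points fewer recorded positives.

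*Tested people only:* both contrasts keep the true direction.

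**When the sign flips.** With all persons as denominator, the difference between two groups is (e2 − e1)·(te·pe − tn·pn). It has the wrong sign whenever tn/te < pe/pn. Here the break-even is 0.3/0.7 = 43%. For 60% v 30% engaged:

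| tn | Difference in recorded positives (points) |
|---|---|
| 0.1 | +6.9 |
| 0.2 | +4.8 |
| 0.3 | +2.7 |
| 0.4 | +0.6 |
| 0.5 | −1.5 |

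The engagement levels set the size, not the sign. With 22% v 45%, nearer to item 3, recorded positives rise by 0.23 × 0.16 = 3.7 points while true use falls by 0.23 × 0.4 = 9.2 points.

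**Second set of assumptions:** te = 0.9, tn = 0.2, pe = 0.4, pn = 0.8; engaged 60% v 22%. Recorded positives are 28.0% v 20.4%, true use is 56.0% v 71.2%, and positives among the tested are 45.2% v 57.6%. If everyone had the same 90% chance of a test, recorded positives would be 50.4% v 64.1%, the correct direction.

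**Repeat testing.** Even among the tested, any positive over several tests grows with their number. Six tests at 15% each give 1 − 0.85⁶ = 62.3%, against 50% from one test at 50%.

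**Chance of a significant reversal.** Assume 100 per group (the documents give no comparator sizes), a two-group contrast and 5% two-sided significance. For 18.8% v 23.6% the standard error is √(0.188·0.812/100 + 0.236·0.764/100) = 0.058, so z = 0.048/0.058 = 0.83 and power is about 13%. For 28.0% v 20.4% it is about 24%.

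**The case against.** A reader might infer that a successful intervention will show more positives and reverse the secondary conclusion. The documents do not support that, for these reasons:

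- **Denominator.** The plan never says that an untested person counts as No X. The percentage could equally be taken among those tested, and then the simple model does not reverse. This stands. It does not rescue the comparison, which remains conditional on selection and exposed to repeat testing. Frequency, also planned, grows with the number of tests under either denominator.
- **ED tests.** Item 1 also names people returning to the ED, whose tests are likely to be positive. They push the other way. If tested non-engaged people were positive 95% of the time (assumed), break-even testing would fall to 0.3/0.95 = 32%. This stands.
- **Engagement of 60%.** It exceeds what item 3 reports even for buprenorphine starters. This stands for the size, but the sign does not depend on it.
- **Significance.** The illustrated reversals would rarely be significant, and a 2-df test across three groups has no direction of its own. This stands.
- **Historical controls.** How their urine was collected is not given here. If it was scheduled, one testing model would not fit all groups.

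A reader might also infer that prescribed buprenorphine or methadone is counted as a positive. The plan is silent, so only the missing definition can be criticised.

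**Conclusion.** The concern holds as a bias of uncertain direction. The documents themselves establish that testing depends on treatment or return to the ED, that no study schedule evens it out, and that item 12 compares recorded positives with no place for untested people. This is more than a missing detail, because the comparison as laid out measures testing as well as use.

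The size is illustrative only. A wrong sign needs the all-persons denominator, raw frequency or repeat testing. On the assumed rates it can work against the intervention (4.8 points up while true use is 12 down) or for it (2.4 points lower while true use is 6 higher). A masked or null result is likelier than a significant reversal. The outcome is secondary and the remedy cheap, so this should be changed but does not threaten the primary aims.

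**What to change.** In items 1 and 12:

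- Report urine results descriptively by group: persons tested, tests per person, and positives among those tested. Drop the confirmatory test of a decrease.
- Show untested people as not tested, never as No X.
- State that a positive means a non-prescribed opioid.
- Rely on self-reported use at days 30 and 180 as the main measure of use in intervention participants; it is already a secondary outcome. Analyse it as reported, without the item 1 rule that EPIC takes precedence. That rule can overturn a denial by a urine result only where a test exists, so it would bring the same bias into this measure.
- Compare self-report between groups only where the comparator has it. The documents do not describe its collection in the concurrent buprenorphine group.

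Reconcile item 11, which lists urine collection among follow-up activities, with Section VI, which makes laboratory testing routine care.

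The cost is some rewording and one secondary hypothesis test given up. No new data collection is needed.
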